PROTOCOL TITLE

Open-Label Prospective Randomized Control Trial to Investigate the Efficacy of Omega-3 Fatty Acid Therapy in Preventing Gastrointestinal Bleeding in Patients with Continuous-Flow Left Ventricular Assist Device

Version: 05Jun2019

NCT03784963

PROTOCOL TITLE

Open-Label Prospective Randomized Control Trial to Investigate the Efficacy of Omega-3 Fatty Acid Therapy in Preventing Gastrointestinal Bleeding in Patients with Continuous-Flow Left Ventricular Assist Device

PRINCIPAL INVESTIGATOR

[name]
Department of Medicine, Section of Cardiology
[contact]

OBJECTIVES

Aim 1: We will evaluate whether high-dose omega-3 fatty acid (O3FA) supplementation alters markers of angiogenesis and inflammation in patients with continuous-flow left ventricular assist devices (CF-LVAD).

- **Aim 1a** will assess the effect of high-dose O3FA in patients who have not experienced an episode of gastrointestinal (GI) bleeding. Patients will be enrolled up to 3 months following CF-LVAD implantation and randomized to high-dose O3FA or none. Markers of angiogenesis and inflammation will be assessed prior to and following initiation of high-dose O3FA therapy.
- **Aim 1b** will assess the effect of high-dose O3FA in CF-LVAD patients who have already experienced a GI bleeding event. Patients who have experienced a prior bleeding event will be enrolled and randomized to high-dose O3FA or none. Markers of angiogenesis and inflammation will be assessed prior to and following initiation of high-dose O3FA therapy.

Aim 2: We will assess the changes that occur to the microbiome of CF-LVAD patients following O3FA supplementation.

Aim 3: We will assess the effect of high-dose O3FA supplementation on GI bleeding events in both the population without prior GI bleeding events, and the population with prior GI bleeding events.

BACKGROUND

Continuous-flow left ventricular assist devices (CF-LVAD) have become the mainstay of therapy for advanced heart failure, both as bridge to transplantation and as destination therapy, allowing significant improvement in survival. However, this therapy is limited by a high adverse event profile, specifically those related to hemocompatibility.

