The data presented thus far shows a possible link between O3FA, GI bleeding, and abnormal angiogenesis, and may be related to the microbiome in CF-LVAD patients. This prospective randomized study aims to evaluate the effect of supplemental O3FA on the frequency of GI bleeding in patients implanted with CF-LVAD both as primary and secondary prevention.

Additionally, we will investigate the effect of O3FA on angiogenesis parameters (Ang-1, Ang-2, VEGF, TNF- α) and the microbiome.

STUDY ENDPOINTS

The primary endpoint will be a change in angiogenesis markers resulting in dysregulated angiogenesis, as described above. Secondary endpoints include rate of GIB and improvement in inflammatory markers.

STUDY INTERVENTION

The study intervention being evaluated is high-dose O3FA (4,000 mg), which is an over-the-counter supplement. Heart failure patients are routinely instructed to take an O3FA supplement for heart health. The research team will fund the supplement, which will be stored in the heart failure office. Once a patient is enrolled, a total of 1 year of supplement will be given to the patient for consumption at home.

PROCEDURES INVOLVED

We will perform an open-label, prospective, randomized control study in which 120 CF-LVAD patients are enrolled. We plan to have 2 separate arms: primary prevention and secondary prevention (60 in each arm). In the primary prevention arm, 60 patients who have received CF-LVAD implantation and have not experienced any episodes of GI bleeding will be assigned to an O3FA group or a control group, with 30 patients in each group. In the secondary prevention arm, 60 LVAD patients who have experienced at least 1 episode of GI bleeding after CF-LVAD implantation will be assigned to an O3FA group or a control group, with 30 patients in each group. Randomization will be performed using computer software, and initiation of therapy will start within 24 hours of randomization. O3FA will be given at a dose of 4,000 mg orally per day, and all patients will receive guideline-directed medical therapy during the study period.

The following study procedures will be performed:

Baseline

Subject to sign consent
Verify inclusion/exclusion criteria
Record medical history and medications
Collect stool sample
Collect blood sample
Randomization
For O3FA subjects:
-Provide O3FA supplement
-Subjects will be instructed to take 4 pills a day

1.5 months post-randomization

Record medical history and medications
Record adverse events

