For O3FA subjects:
-Provide O3FA supplement
-Subjects will be instructed to take 4 pills a day
-Study drug compliance check

3 months post-randomization

Record medical history and medications

Collect stool sample

Collect blood sample

Record adverse events

For 03FA subjects:

- Provide O3FA supplement

- Subjects will be instructed to take 4 pills a day

- Study drug compliance check

4.5 months post-randomization

Record medical history and medications

Record adverse events

For 03FA subjects:

- Provide O3FA supplement

- Subjects will be instructed to take 4 pills a day

- Study drug compliance check

6 months post-randomization

Record medical history and medications

Collect stool sample

Collect blood sample

Record adverse events

For 03FA subjects:

- Provide O3FA supplement

- Subjects will be instructed to take 4 pills a day

- Study drug compliance check

7.5 months post-randomization

Record medical history and medications

Record adverse events

For 03FA subjects:

- Provide O3FA supplement

- Subjects will be instructed to take 4 pills a day

- Study drug compliance check

9 months post-randomization

Record medical history and medications

Record adverse events

For 03FA subjects:

- Provide O3FA supplement

- Subjects will be instructed to take 4 pills a day

- Study drug compliance check

10.5 months post-randomization

Record medical history and medications

Record adverse events

For 03FA subjects:

- Provide O3FA supplement

- Subjects will be instructed to take 4 pills a day

- Study drug compliance check

1 year post-randomization

Record medical history and medications

Collect stool sample

Collect blood sample

Record adverse events

For O3FA subjects:

-No more O3FA supplements will be provided by the study

-Study drug compliance check

Stool Collection for Microbiome Sequencing Analysis

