Statistical analysis will be performed using SPSS Statistics 22 (SPSS Inc, Chicago, IL, USA). Variables with 2-tailed p value <0.05 will be considered significant. Clinical parameters and outcomes including rates of GI bleeding, angiogenesis-related biomarkers, inflammatory markers, and microbiome data will be compared between the O3FA and control groups, both among the primary and secondary prevention arms using unpaired t-test or Mann-Whitney U test as appropriate. A necessary patient number for each group is calculated as 26 (total 104) by power analysis with 0.05 of α , 0.8 of effect size, 0.8 of $1-\beta$.

A master list maintaining patient names and code numbers will be stored in locked files. A password-protected computer located in the heart failure main office will contain a database for data collected in this study. Case report forms (CRF's) will be generated and filled out for each subject enrolled in this study.

There is a risk of loss of confidentiality. If a patient agrees to participate, and signs an informed consent, a signed copy of the consent will be given to them, a copy placed in their record and then the data will be abstracted into an electronic database. The database will be within the Department of Medicine, Section of Cardiology. The data will be password protected and covered by all of the firewalls and security features of the Department of Medicine.

The investigators seek to minimize these risks by labeling the study related data and specimens with a study code. This study code will be linked with the patient's data. Only the investigators

and their designated staff will have access to the databases and the link between study code numbers and patient identifying information.

Data and samples may be utilized by faculties who have the proper IRB approval to do so, and whose study objective meets with the overall objective of this research.

We may share coded data and/or samples outside of the institution in collaboration efforts. An IRB amendment will be submitted to the IRB for review if this happens. Additionally, if NIH funding is obtained for any proposed study, it is possible that the PI will be required to provide a copy of coded data to the NIH for public use. In either case, direct patient identifiers will never be shared.

ECONOMIC BURDEN TO PARTICIPANTS

There will be no economic burden to the participants.

CONSENT PROCESS

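### The baseline marker value is collected but not used as a covariate in the primary comparison; baseline-adjusted analysis would be more precise at no extra sampling cost

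*Combined protocol and SAP*

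**What the plan says.** - *Study Endpoints*: "The primary endpoint will be a change in angiogenesis markers resulting in dysregulated angiogenesis".
- *Objectives*, Aims 1a and 1b: "Markers of angiogenesis and inflammation will be assessed prior to and following initiation of high-dose O3FA therapy".
- *Procedures Involved*: the instruction "Collect blood sample" appears at baseline, listed ahead of randomisation, and again at 3 months, 6 months and 1 year. It is not restricted to the O3FA group.
- *Statistical Analysis, Data Management, and Confidentiality*: biomarkers are compared between O3FA and control "both among the primary and secondary prevention arms using unpaired t-test or Mann-Whitney U test as appropriate". On significance: "Variables with 2-tailed p value <0.05 will be considered significant". On size: "A necessary patient number for each group is calculated as 26 (total 104) by power analysis", with an effect size of 0.8 and power of 0.8.
- *Procedures Involved* sets enrolment at 30 per group in each of two prevention arms, 120 in all.

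No regression, ANCOVA, repeated-measures model or other covariate adjustment appears anywhere. The plan does not say whether the tested variable is the follow-up value or the within-patient change, which of the three follow-up draws is used, or which SD the effect size of 0.8 refers to.

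**The concern.** With a marker measured before randomisation and again afterwards, an unadjusted two-sample test can be run in two ways. Run on follow-up values, it ignores baseline, which amounts to fixing the baseline slope at 0. Run on changes, it fixes the slope at 1. With equal variances at the two times this over-corrects chance baseline imbalance whenever the baseline-to-follow-up correlation ρ is below 1, and it is noisier than ignoring baseline when ρ is below 0.5. ANCOVA estimates the slope from the data.

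What is at stake is precision in two small, separately analysed comparisons of 30 against 30. Because the tested variable and the SD behind 0.8 are both undefined, the power that enrolment buys depends on how the plan is read. In addition, no model combines the three follow-up draws.

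**Working it through.** **Inputs.** From the statistical section: two-sided α = 0.05, effect size 0.8, power 0.80, 26 per group. From *Procedures Involved*: n = 30 per group. Assumed, because the documents do not give them: ρ = 0.3, 0.5 or 0.7, equal variances at baseline and follow-up, and complete data.

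**1. The plan's own figure.** For an unpaired t-test, power comes from a noncentral t with df = 2n − 2 and noncentrality d√(n/2).

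- The exact solution for d = 0.8 and 80% power is n = 25.52, rounded up to 26. At n = 26 the noncentrality is 0.8 × √13 = 2.884 and power is 0.807. Four groups of 26 make 104, so the stated figure reproduces.
- At n = 30 the noncentrality is 0.8 × √15 = 3.098 and power is 0.861.

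The sample size therefore rests on an unadjusted test and takes no account of baseline.

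**2. Variance of each analysis**, relative to testing follow-up values:

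- follow-up value: 1
- change score: 2(1 − ρ)
- ANCOVA: 1 − ρ², with one degree of freedom fewer (df = 2n − 3)

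Relative to the change score, ANCOVA has variance (1 − ρ²) / [2(1 − ρ)] = (1 + ρ)/2, which is below 1 for every ρ below 1.

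**3. Reading A: 0.8 is in SDs of the follow-up value.** The effective d is 0.8 divided by the square root of the variance factor. Example at ρ = 0.5: 0.8/√0.75 = 0.924; noncentrality 0.924 × √15 = 3.58; power 0.940.

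| ρ | Follow-up only: n for 80%; power at 30 | Change score: n; power at 30 | ANCOVA: n; power at 30 |
|---|---|---|---|
| 0.3 | 26; 0.861 | 36; 0.731 | 24; 0.891 |
| 0.5 | 26; 0.861 | 26; 0.861 | 20; 0.940 |
| 0.7 | 26; 0.861 | 16; 0.976 | 14; 0.989 |

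**4. Reading B: 0.8 is in SDs of the change.** The change score then has n = 26 and power 0.861 at 30, whatever ρ is. ANCOVA uses d = 0.8/√[(1 + ρ)/2].

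| ρ | Change score: n; power at 30 | ANCOVA: n; power at 30 |
|---|---|---|
| 0.3 | 26; 0.861 | 17; 0.965 |
| 0.5 | 26; 0.861 | 20; 0.940 |
| 0.7 | 26; 0.861 | 22; 0.910 |

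**5. Allowing for chance baseline imbalance.** The ANCOVA figures above treat the groups as balanced at baseline. In a randomised trial the variance of the adjusted difference is inflated by 1 + t²/(2n − 2), where t is the two-sample t statistic for baseline. Averaging power over its t distribution (2n − 2 df) gives:

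- Reading A: power at 30 of 0.886 / 0.936 / 0.988; n = 24 / 20 / 15.
- Reading B: power at 30 of 0.963 / 0.936 / 0.906; n = 18 / 20 / 23.

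Every power figure moves by less than 1 point.

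**6. Low correlation, reading A, n = 30, imbalance allowed for.**

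| ρ | Follow-up only | Change score | ANCOVA |
|---|---|---|---|
| 0 | 0.861 | 0.577 | 0.855 |
| 0.1 | 0.861 | 0.622 | 0.859 |
| 0.2 | 0.861 | 0.673 | 0.869 |

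**7. Validity.** Simulation under reading A (40,000 trials per cell, 30 per group) gave ANCOVA power of 0.884 / 0.936 / 0.988 at ρ = 0.3 / 0.5 / 0.7, and type I error of 0.048 to 0.052 for all three tests. The issue is efficiency alone.

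**The case against.** The best case for the plan is that nothing in it is wrong. The unadjusted test is valid under randomisation, 26 per group is correct for it, and 30 per group gives 86% against a target of 80% if 0.8 refers to the variable tested. That stands, and it is why this is an improvement and not an error.

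The gain also depends wholly on a correlation the documents do not supply. It could be low in the primary prevention arm: Aim 1a enrols up to 3 months after implantation and the inclusion criteria admit patients still awaiting a device, so some baselines may precede or closely follow surgery. This stands too. At ρ of 0.1 to 0.2, ANCOVA is practically level with a test on follow-up values (0.859 and 0.869 against 0.861). Low ρ is not an argument for the plan as written, however, because a change score then does worst under reading A.

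The 58 to 73% power figures for a change score at ρ of 0.3 or less require a mismatch: changes are tested while 0.8 is in follow-up SDs. An effect size more naturally refers to the variable tested, and the endpoint is worded as a change, which favours reading B. That is fair, and those figures describe one scenario, not the expected outcome. Under reading B the change score has its 86%, but subtraction still leaves precision unused, and ANCOVA gains about 4 to 10 points over the range shown.

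Finally, ANCOVA cannot be written down until a marker and visit are chosen, and the blood-collection section lists 13 angiogenesis factors. A log or rank scale also changes what is estimated. Both points are true; they shape the fix without removing the gain.

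**Conclusion.** The concern holds. The primary marker comparison leaves out a baseline covariate that the trial already collects, and the plan leaves open which variable is tested.

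Under equal variances, complete data and ρ between 0.3 and 0.7, adjustment lifts power at 30 per group from 86% to about 89–99% (reading A, against follow-up values) or about 91–96% (reading B, against the change score). In patients, the unadjusted test needs roughly 2 to 12 more per group for 80% power under the simple formula (26 against 24 / 20 / 14 or 17 / 20 / 22).

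The omission is certain; the size of the benefit is not, because ρ and the SD behind 0.8 are assumptions. The downside is small: at ρ = 0, power falls from 86.1% to 85.5%. The change should be made.

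**What to change.** 1. State the primary marker, the visit, and whether the endpoint is the follow-up value or the change. State which SD the effect size of 0.8 refers to.
2. Within each prevention arm, replace the unpaired test on markers with ANCOVA of the follow-up value at the named visit on randomised group and the baseline value of the same marker. Use the log scale, or rank ANCOVA, if the marker is skewed, and fix that choice in advance. A mixed model over 3, 6 and 12 months with baseline and baseline-by-visit terms is an acceptable alternative.
3. Report the adjusted difference, or the geometric-mean ratio on the log scale, with its 95% confidence interval.
4. Keep the Mann-Whitney U test as a sensitivity analysis.
5. Keep the planned enrolment and take the gain as power. Because ρ is unknown, it should not be used to reduce numbers, and the withdrawal section erases withdrawn participants' data, so fewer than 30 per group may be analysed.

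**Cost.** Revised analysis wording and, for ANCOVA, one degree of freedom per comparison. The mixed model or a transformed scale needs a few more prespecified choices. No extra patient, visit, blood draw or assay is needed.

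### Markers are sampled at 3, 6 and 12 months, but the plan names only a one-value-per-patient test, with no visit, summary over visits, baseline adjustment or repeated-measures model

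*Combined protocol and SAP*

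**What the plan says.** The section on study endpoints states: "The primary endpoint will be a change in angiogenesis markers resulting in dysregulated angiogenesis, as described above". It names no marker, visit or summary. Aim 1 refers only to assessment before and after therapy starts.

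The visit schedule under Procedures Involved has a blood draw at baseline, at 3 months, at "6 months post-randomization" and at "1 year post-randomization". The visits in between have none.

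The statistical analysis section compares biomarkers between O3FA and control "both among the primary and secondary prevention arms using unpaired t-test or Mann-Whitney U test as appropriate". The significance rule is "Variables with 2-tailed p value <0.05 will be considered significant". The sample size statement reads "A necessary patient number for each group is calculated as 26 (total 104", with "0.8 of effect size", alpha 0.05 and power 0.8. Enrolment is 30 v 30 in each prevention arm.

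No repeated-measures model, baseline covariate or rule for a missed sample appears anywhere. The withdrawal section says that all data of a participant who withdraws, or is withdrawn for not taking O3FA, are permanently erased.

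**The concern.** The design pays for three follow-up measurements per patient, while the analysis is described as if there were one. The analyst must then choose among a single visit, each visit in turn, a change score or a mean over visits. Testing each visit gives three answers at 5% each and no rule for disagreement between them. Testing one visit leaves two-thirds of the follow-up marker values out of the primary comparison and, by the default behaviour of these tests, omits any patient without that sample.

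With 30 per group, precision is scarce. A choice among these analyses made after the data are seen would also weaken the primary result.

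**Working it through.** **Inputs from the documents.** Two-sided alpha 0.05, power 0.8, standardised effect 0.8, 26 per group required, 30 v 30 enrolled per prevention arm, follow-up blood at 3, 6 and 12 months.

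**Assumed.** The correlation r between any two samples of one patient is not given. I take it as equal for all pairs and vary it from 0.3 to 0.9. A single raw value has variance 1, and no data are missing unless stated.

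**Step 1: the plan's figure.** A two-sided two-sample t-test at effect 0.8 and power 0.8 needs 25.52 per group, rounded up to 26. This matches the plan, so the sample size is that of a test on one value per patient. Power at 0.8 SD is 80.7% with 26 per group and 86.1% with 30.

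**Step 2: variance with one visit and with three.** Each row compares like with like.

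| Analysis | One visit | Mean of three visits | Cut at r = 0.3 / 0.5 / 0.7 / 0.9 |
|---|---|---|---|
| Unadjusted value | 1 | (1+2r)/3 | 47% / 33% / 20% / 7% |
| Change from baseline | 2(1-r) | (1+2r)/3 + 1 - 2r | 33% at every r |
| Baseline-adjusted | 1 - r² | (1+2r)/3 - r² | 51% / 44% / 39% / 35% |

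For the last row at r = 0.5: one visit 1 - 0.25 = 0.75; three visits 0.667 - 0.25 = 0.417; cut 1 - 0.417/0.75 = 44%. At r = 0.7: 0.51 and 0.31, cut 39%. In standard error, the cuts in this row are 30% / 25% / 22% / 19%.

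**Step 3: power, 30 v 30, r = 0.5.** Divide the effect by the square root of the variance and use the noncentral t.

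| True effect | One raw value | One visit, baseline-adjusted | Three-visit mean, baseline-adjusted |
|---|---|---|---|
| 0.5 SD | 48% | 59% | 84% |
| 0.8 SD (the plan's) | 86% | 94% | over 99% |

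An unadjusted three-visit mean has 64% power at 0.5 SD.

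**Step 4: where averaging costs power.** Take 0.6 SD at 12 months, r = 0.5, 30 v 30, both analyses baseline-adjusted.
- Steady build-up (1/3, 2/3, 1 of the effect): the average effect is 0.4 SD. Power is 66% for the average and 75% at 12 months.
- Effect at 12 months only: the average effect is 0.2 SD. Power is 22% and 75%.

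**Step 5: if only the 12-month difference matters.** Let d be the fraction missing at 12 months, at random, and e = 1 - 3r²/(1+2r) the variance left given baseline, 3 and 6 months. Completers have variance (1-r²)/(1-d); the mixed model has (1-r²-e) + e/(1-d).
- r = 0.5, d = 0.1: 0.833 v 0.819, a saving of 2%.
- r = 0.7, d = 0.3: 0.729 v 0.676, a saving of 7%.

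**Step 6: another correlation pattern.** Let the correlation fall with time, at r per 3 months. Against a baseline-adjusted 12-month test the cut is 53-56% for r = 0.5-0.9. Against a 3-month test it is 12% at r = 0.7 (0.51 v 0.447), and at r = 0.9 the average is worse (0.19 v 0.253).

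**The case against.** The strongest reply is that an unpaired test needs one number per patient, not one visit. That number could be a mean or mean change over the three visits, and most of the gain comes from averaging rather than from the mixed model. This stands. A reader might infer that the plan commits to a single visit and drops everyone without it. The documents say neither: they leave the summary and the handling of missed samples open, and the omission is only what these tests do by default.

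A reader might also infer that the plan wastes some fixed share of its precision, such as about 40%. The documents do not support that. Any such figure needs a correlation they do not give and an averaged target, and a cut of about 40% at r of 0.6-0.7 also presumes baseline adjustment that the plan does not mention. Against an unadjusted single value, the saving can be as small as 7%.

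At the plan's own 0.8 SD there is less to gain. One raw value already has 86% power with 30 v 30, and once baseline is adjusted for, averaging adds about 6 points at r = 0.5 and 1 at r = 0.7. The larger gains appear at effects smaller than the plan assumed.

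The documents give no time course for the effect, so the choice of the average is a judgement.

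Finally, earlier samples from everyone who leaves might seem to be available to a mixed model. They are not: withdrawn participants' data are erased. The non-compliance trigger can fall only on the O3FA group, and no model recovers erased values. The missing-data benefit is confined to patients who miss samples without being withdrawn, and their number is not stated.

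**Conclusion.** The point holds as a gap in specification with a cheap and more efficient remedy. The planned test is not invalid, but the plan does not say what enters it, and the sample size ignores the repeated draws. The gain in precision is conditional on the average over follow-up being the target and on the assumed equal correlation. For a contrast at 12 months alone, baseline adjustment brings nearly all the gain; the extra visits add about 2-7% with 10-30% missing, and nothing with complete data. This should be changed before analysis.

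**What to change.** For markers, replace the unpaired test with a baseline-adjusted mixed model for repeated measures, fitted within each prevention arm to the log-transformed 3-, 6- and 12-month values. Terms: baseline, visit, treatment and treatment-by-visit, with unstructured covariance. Include every patient with at least one retained follow-up sample.

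Name the primary marker and one main contrast before any data are seen. The treatment difference averaged over the three visits is suggested, with visit-specific differences secondary. If the team expects a late effect, it should choose the 12-month contrast from the same model instead, given the losses in Step 4.

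State how missed samples are handled. Amend the erasure rule so that data collected before withdrawal are kept where consent allows; otherwise the model cannot use them.

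The model costs a few sentences in the statistical section and one mixed-model procedure in SPSS, the software already named. It needs no new samples. The change to data retention would also need matching consent wording.
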